9.3.2 Longitudinal Model of 12-month VABS-3 Mortality Composite Score

At each interim analysis there will be participants who have not yet reached 12-months and will therefore not have a final outcome. We use the 3-month VABS-3 Mortality Composite Score as possibly predictive of the 12-month score, allowing participants with this earlier measurement to be included in the analyses of the 12-month measurement. This modeling is referred to as the longitudinal model. The longitudinal model allows for learning the relationship between the 3-month and 12-month VABS-3 Mortality Composite Scores as the accruing empirical data is used to determine the strength of the association between the two values. The observed 12-month values are augmented by multiple imputations from the longitudinal model (simple linear regression) for participants with an unknown 12-month value.

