3.1 Clinical Sites

At all participating sites, the usual clinical practice during the course of P-ICECAP for comatose pediatric OHCA survivors will be rapid initiation of TTM to a target within the local temperature range on arrival in the

[figure not shown]
pediatric intensive care unit (PICU); any definitive servo-regulated surface temperature control device may be used. Approximately 70 percent were former sites in the THAPCA trials. Approximately 45 hospitals are anticipated to each enroll an average of 4 participants per year. The enrollment period is anticipated to be 5 years (estimated accrual rate of 15 participants per month).

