3.2 Randomization and allocation

Central computerized randomization by web-based interface will be used. Participants will be potentially randomized over the course of the trial to the following possible durations of cooling (in h): 0, 12, 18, 24, 36, 48, 60, 72, 84 and 96. The first 150 participants will be randomized 1:1:1 to the 24, 48, and 72-hour durations only. After this initial “burn in” period, response adaptive randomization will be used to allocate participants to other durations if the emerging duration-response curve (DRC) suggests that the largest treatment benefit might be on those durations. Randomization probabilities will be updated about every 10 weeks. At an expected accrual rate of 15 participants per month, 37 (range 30-45) interim participants would be projected. The 3-month VABS-3 Mortality Composite Score will be used in longitudinal modeling for adaptive randomization until the 12-month value is obtained. We have previously reported the 3- and 12-month VABS-II to be highly correlated ($r=0.95$) in the THAPCA trials (Slomine, 2019).

After the burn in period, the trial can open all arms. Allocation procedures are described in greater detail in Section 9 and in the Statistical Design appendix. Arms where the model proposes less than 5% allocation will be temporarily set to zero until the next interim look.

All of the possible durations that will be tested from 0 to 96 h are shown in the white shapes on the left in figure. The sequential columns of red circles represent randomization vectors as the trial progresses and participants accrue in the trial. After the burn-in period, shorter, longer, and interspersed arms may receive some allocation depending on the shape of the emerging DRC. The blue arrows at the top indicate automated “looks” at the data about every 10 weeks. At each look, there is a test for efficacy and futility and then calculation of the new randomization vector.

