6. OUTCOMES

6.1 Primary Efficacy Outcome

Primary Efficacy Outcome. The primary outcome will be the “VABS-3 Mortality Composite Score” in which enrolled participants who die before the 12-month outcome are scored 0 and the age-adjusted standardized VABS-3 composite score is assigned for the survivors (Sparrow , 2016). Measured VABS-3 composite scores range from 20-140 (mean=100, SD=15). The VABS-3 Mortality Composite Scores will be compared across treatment groups at 12 months after OHCA. The VABS-3 measures three core domains of neurobehavioral function (communication, daily living, socialization). These 3 core domains yield age-corrected standardized scores that contribute equally to an overall adaptive behavior composite score. The VABS-3 is applicable from birth through adulthood and has strong reliability and validity in children of all ages. Of note, no NIH toolbox neurobehavioral outcome measures are validated for children under age 3, and the measures for pre-school children function poorly for those with significant impairments.

The previous version of the Vineland (VABS-II) (Sparrow, 2005) was used as the primary outcome for the THAPCA trials and is no longer available. The new VABS-3 has updated content to reflect changes in everyday

life (e.g., new technology) and provides an online administration format using a computer or tablet that guides the examiner in the structured interview process by tracking item content and applying basal and ceiling rules.

In survivors, VABS-3 data will be obtained, using this format for structured telephone interviews, scheduled at 3 and 12 months after OHCA. Data will be collected by a trained interviewer, unaware of treatment allocation, at a central outcome center (KKI) with extensive experience and familiarity with this tool and method of data collection. Each interview is expected to take 30 to 45 minutes. The VABS-3 item content is available in English and Spanish. Spanish speaking interviewers will interview Spanish speaking caregivers.

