9.4 Adaptive Randomization

The first 150 participants will be equally randomized to the 24, 48, and 72-hour arms. After this initial randomization period, adaptive randomization will begin. Randomization probabilities to each treatment arm are weighted according to the weighted average of two posterior probabilities: the posterior probability that each treatment arm produces the maximum treatment effect (25% weight) and the posterior probability that each treatment arm produces 95% of the maximum treatment effect (75% weight). The target duration and randomization probabilities will be updated approximately every 10 weeks. The goal of the adaptive randomization is to allocate participants to the arms most likely to be the target duration, but also to learn effectively about the duration-response curve.

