9.5 Interim Monitoring for Efficacy and Futility

Interim analyses begin after 150 participants have been enrolled and will occur approximately every 10 weeks. At each interim analysis, the trial may stop accrual for expected futility if the 0-hour cooling period has at least an 85% probability of being the cooling period with maximum treatment benefit. At each interim analysis, the trial may stop accrual for expected success if the 96-hour cooling period has at least a 95% probability of being the cooling period with maximum treatment benefit. If a futility or efficacy stopping rule is met at an interim analysis, then a final analysis will be conducted after all currently enrolled participants have been followed to their final endpoint.

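### Does the interim longitudinal model make newly opened arms look falsely bad by counting deaths before survivors can be scored?

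*Protocol*

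**What the plan says.** The primary outcome is the VABS-3 Mortality Composite Score. Under Section 6.1, "enrolled participants who die before the 12-month outcome are scored 0", and survivors receive their measured score from interviews "scheduled at 3 and 12 months after OHCA". The schedule in Section 6.4 lists the composite itself, not only the interview, at both times.

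On timing, Section 9.4 states that "The first 150 participants will be equally randomized to the 24, 48, and 72-hour arms". Section 9.5 adds that "Interim analyses begin after 150 participants have been enrolled and will occur approximately every 10 weeks", and Section 3.2 that "Randomization probabilities will be updated about every 10 weeks". Section 3.1 gives an "estimated accrual rate of 15 participants per month".

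For participants short of 12 months, Section 9.3.2 uses the 3-month composite as a predictor: "The observed 12-month values are augmented by multiple imputations from the longitudinal model (simple linear regression) for participants with an unknown 12-month value". Section 3.2 likewise says that the 3-month composite serves in the longitudinal modelling until the 12-month value is available. Neither section says on which date a death enters the interim data, or what is done with a child who is alive and has no 3-month score yet. Sections 3.2 and 9 refer to a Statistical Design appendix and the SAP for further detail.

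**The concern.** The two components of the composite become known at different speeds. A zero is certain at death, and most deaths come early. A survivor's value cannot be seen, or predicted by a regression on the 3-month score, for about 13 weeks. Looks are 10 weeks apart, so at the first look after an arm opens, no survivor in it can have a score.

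If deaths were entered at once and unscored survivors were left out, inclusion would depend on the outcome, and most strongly in the youngest arms. Both early stopping rules in Section 9.5 concern arms outside the burn-in (0 h for futility, 96 h for success). Section 3.2 also sets to zero, until the next look, any arm whose proposed allocation is below 5%. A falsely low start could therefore distort allocation and delay a justified stop.

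Two further doubts concern the regression. A straight line through a mass of zeros and survivor scores of 20 to 140 looks like the wrong model. At the first look there may also be no survivor with both scores from which to fit it.

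**Working it through.** **Plan's own figure.** Composite mean = survival × mean score in survivors. No effect: 0.45 × 65 = 29.25 (stated 29.3). Full effect: 0.55 × 75 = 41.25 (stated 41.3). Difference: 12.0, as Section 9.7 states.

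**How early deaths fall.** 28-day mortality in THAPCA-OH was 57% (hypothermia) and 67% (normothermia) (Section 6.2), and 12-month survival was 38% and 29% (Background). The share of 12-month deaths by day 28 is therefore 57/62 = 92% and 67/71 = 94%. I take 93%, spread evenly over 4 weeks, with the rest spread evenly to week 52. As a sensitivity case I take 80%.

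**Reading A: deaths enter at once, unscored survivors are left out.** For an arm open T weeks with even accrual, let h be the share of its participants past 13.04 weeks. Then

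expected interim mean = h × true mean / (share dead so far + share alive and past 13.04 weeks).

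At T = 20 with true mean 29.25: h = 6.96/20 = 0.348, share dead = 0.465, share alive and scored = 0.167. The mean is 0.348 × 29.25 / 0.632 = 16.1.

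| Weeks open | New arm, true mean 29.25 | New arm, true mean 41.25 | Burn-in arms, true mean 29.25 |
|---|---|---|---|
| 10 | 0 | 0 | 26.4 |
| 20 | 16.1 | 24.7 | 27.0 |
| 30 | 21.9 | 32.4 | 27.3 |
| 40 | 24.2 | 35.2 | 27.5 |

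The burn-in column assumes 150 participants accrued over 43.5 weeks and then 70% of later accrual, with 30% going to the new arm. With no true difference, the false gap at 20 weeks is 27.0 − 16.1 = 10.9. With 80% early deaths it is 27.3 − 17.1 = 10.2. These are raw arm means. The shared duration-response curve would damp them by an amount that cannot be computed without the priors.

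**Reading B: everyone, dead or alive, enters at the 3-month date.** Entry then depends on calendar time alone. Both the numerator and the denominator carry the factor h, so the expected mean is h × 29.25 / h = 29.25 in every arm of every age. At 10 weeks a new arm contributes nothing, which is neutral.

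**Which reading the text supports.** Section 9.3.2 describes anyone short of 12 months as lacking a final outcome and admits them through the 3-month measurement. That measurement is the composite, with death already scored 0. Section 3.2 keeps using it until the 12-month value exists. Both point to Reading B. Nothing says that a death enters on the day it occurs.

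**Is the straight line adequate?** I simulated one million participants: survival 45%, survivor mean 65, SD 20 (assumed), 3-to-12-month correlation 0.95 in survivors (Section 6.1 gives 0.95 for composite scores), 93% early deaths. The pooled line has intercept 0.2 and slope 0.93. In those alive at 3 months it predicts a mean of 60.7 against a true 60.9. With 80% early deaths the figures are 54.1 and 54.3. Even if known deaths were imputed from the line, their mean would be 0.2. The overall correlation is 0.936 and about 52% are dead by 3 months, so the added variance would be about (1 − 0.936²) × 0.52 = 0.064, or 6%.

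**First look.** 150/15 = month 10, so no participant has reached 12 months. At the next two looks (months 12.3 and 14.6) the numbers past 12 months are 0.3 × 15 ≈ 5 and 2.6 × 15 = 39.

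**The case for a change.** The strongest case is that Section 9.3.2 goes beyond silence. It names the imputation method and says that it covers participants with an unknown 12-month value, and a regression on the 3-month score cannot cover a survivor who has none. A programmer could fairly treat a death as a known 12-month value and a recent survivor as missing, and would then produce Reading A. The two readings differ by nearly the whole design effect at 20 weeks, in the arms on which early stopping depends, and one sentence would settle the matter.

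What stands is that the entry date is not written in the protocol and that Reading A would be a real error. It does not follow that the plan is wrong. The text leans to Reading B, and the handling of partly followed participants, with the priors for the longitudinal model, is ordinary SAP content.

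The point about the first look also stands in part: imputation there must rest on a prior that the protocol does not give. However, 15 per month is the five-year average (900/60). Section 9.12 describes an initial approval limited to 50 participants, so a slower start and a later first look, with more 12-month scores, are likely. If one line is fitted for all arms, as the text implies, a weak early fit does not single out new arms.

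A separate model for death between 3 and 12 months would be a legitimate choice, but it would remove a mean error of about 0.2 points.

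**Conclusion.** The concern does not call for a change. The bias is real only if deaths are counted on the day they occur while unscored survivors are dropped. It would then be about 10 to 11 points at 20 weeks, before smoothing. The protocol does not prescribe that rule, and its description of the 3-month composite as the route into the interim analysis points to the rule under which the expected bias is zero. On the assumptions shown, the linear regression is accurate to about 0.2 points on average.

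What remains is a gap that analysts fill sensibly: the date on which a death enters, and the handling of survivors with no 3-month score. The effect is confined to allocation and early stopping, because Section 9.5 places the final analysis after all enrolled participants have been followed to their endpoint.

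The conclusion assumes mortality timing like that of THAPCA-OH, a survivor SD near 20, and one regression for all arms. How far futility or early success would shift under Reading A cannot be derived from the protocol, which gives neither the priors nor the SD, so no figure is offered.

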9.4 Adaptive Randomization

The first 150 participants will be equally randomized to the 24, 48, and 72-hour arms. After this initial randomization period, adaptive randomization will begin. Randomization probabilities to each treatment arm are weighted according to the weighted average of two posterior probabilities: the posterior probability that each treatment arm produces the maximum treatment effect (25% weight) and the posterior probability that each treatment arm produces 95% of the maximum treatment effect (75% weight). The target duration and randomization probabilities will be updated approximately every 10 weeks. The goal of the adaptive randomization is to allocate participants to the arms most likely to be the target duration, but also to learn effectively about the duration-response curve.

9.5 Interim Monitoring for Efficacy and Futility

Interim analyses begin after 150 participants have been enrolled and will occur approximately every 10 weeks. At each interim analysis, the trial may stop accrual for expected futility if the 0-hour cooling period has at least an 85% probability of being the cooling period with maximum treatment benefit. At each interim analysis, the trial may stop accrual for expected success if the 96-hour cooling period has at least a 95% probability of being the cooling period with maximum treatment benefit. If a futility or efficacy stopping rule is met at an interim analysis, then a final analysis will be conducted after all currently enrolled participants have been followed to their final endpoint.

9.6 Sample Size

This trial will enroll a maximum of 900 participants. If the trial is not stopped early for futility or efficacy, it will continue to enroll to the maximum sample size. Extensive numerical simulations of the design were conducted over a range of potential scenarios to characterize the trial's Type I error and the power for the primary analysis provided by a maximum of 900 participants. Sensitivity of operating characteristics to a range of sample sizes was also simulated.

9.7 Power and Type I Error Control

For trials with adaptive features like those presented here, asymptotic formulas are not available to calculate operating characteristics (e.g., power, expected sample size). We evaluate the proposed design through trial simulation. We hypothesize several possible underlying true settings (referred to here as scenarios) for the mean response. For each of these scenarios, we generate data according to the true distribution in the scenario and run through the entire design as specified above. We repeat this process to create multiple virtual trials, tracking the behavior of each trial and then summarizing characteristics over the many simulations. The assumed effect sizes in these scenarios were based on historic THAPCA-OH observed effects as well as effects seen in other cooling studies. Additional information can be found in the SAP.

To demonstrate the variety of duration-response scenarios considered in the simulation study, seven examples are provided in TABLE 9.7.A. A name briefly describing each scenario, the overall VABS-3 Mortality Composite Score, and the survival and average VABS-3 among survivors are presented. In the scenarios described by plateau at 48 and 72 hours, constant upslope, and (inverted) U-shape, the effect size is an increase in survival of 10% and an increase of 10 on the VABS-3 among survivors. This corresponds to an increase from 29.3 to 41.3 (12 units) on the VABS-3 Mortality Composite Score. The different scenarios reflect when/how we might observe those peaks. The scenario described by a plateau at 72 hours with a larger effect corresponds to an increase of about 19 units on the VABS-3 mortality composite score.

Table 9.7.A: Scenarios evaluated for operating characteristics in P-ICECAP

Scenario	Outcome Component	Arm (Cooling Duration in Hours)									
		0 ⁰	12	18	24	36	48	60	72	84	96
Null	Overall	29.3	29.3	29.3	29.3	29.3	29.3	29.3	29.3	29.3	29.3
	Survival (%)	45	45	45	45	45	45	45	45	45	45
	VABS-3	65	65	65	65	65	65	65	65	65	65
Plateau at 48 hours	Overall ¹	29.3	31.5	33.8	36.2	38.7	41.3	41.3	41.3	41.3	41.3
	Survival (%)	45	47	49	51	53	55	55	55	55	55
	VABS-3 ²	65	67	69	71	73	75	75	75	75	75
Plateau at 72 hours	Overall ¹	29.3	31.0	32.4	33.8	35.6	37.4	39.3	41.3	41.3	41.3
	Survival (%)	45	47	48	49	50.5	52	53.5	55	55	55
	VABS-3 ²	65	66	67.5	69	70.5	72	73.5	75	75	75
Plateau at 72 hours (larger effect)	Overall ¹	29.3	30.9	32.6	35.0	38.1	41.3	44.6	48.0	48.0	48.0
	Survival (%)	45	46.5	48	50	52.5	55	57.5	60	60	60
	VABS-3 ²	65	66.5	68	70	72.5	75	77.5	80	80	80
Constant Upslope	Overall ¹	29.3	31.5	32.6	33.8	35.0	36.2	37.4	38.7	40.0	41.3
	Survival (%)	45	47	48	49	50	51	52	53	54	55
	VABS-3 ²	65	67	68	69	70	71	72	73	74	75
U-Shaped	Overall ¹	29.3	31.5	33.8	36.2	38.7	41.3	41.3	41.3	35.0	29.3
	Survival (%)	45	47	49	51	53	55	55	55	50	45
	VABS-3 ²	65	67	69	71	73	75	75	75	70	65
Harmful	Overall ¹	29.3	28.2	27.3	26.5	25.6	24.8	24.00	23.2	22.4	21.6
	Survival (%)	45	44	43	42	41	40	39	38	37	36
	VABS-3 ²	65	64	63.5	63	62.5	62	61.5	61	60.5	60

⁰ Controlled Normothermia ¹VABS-3 Mortality Composite Score VABS-3 among survivors

For each of the scenarios described in TABLE 9.7A, we simulated 10,000 virtual trials and tracked the behavior of each trial, including the final outcome, the observed sample size, and selected duration of cooling that achieves 95% of the maximum treatment effect (ED95). In TABLE 9.7B, the results are summarized across all 10,000 simulated trials for each scenario. We define power as the proportion of trials that identify a positive effect of cooling based on the duration response curve, regardless of the selected target duration. Success on Aim 2 is clinically defined by selecting an ED95 that is within 1 or 2 durations of the true ED95. Early stopping for efficacy occurs when there is overwhelming evidence that the 96-hour cooling duration provides the best clinical effect. Late efficacy is defined when the trial does not stop early and the final analysis concludes that there is evidence increasing durations of cooling are associated with better outcomes.

Table 9.7.B: Operating characteristics of tested scenarios for the P-ICECAP trial

Scenario	Expected Sample Size	Aim 1 Power			Futility	Aim 2 Power - Proportion of Trials	
		Overall	Early Efficacy	Late Efficacy		Correctly Choose ED95 ± 1 Duration	Correctly Choose ED95 ± 2 Duration
Null	848	4.6	0.5	4.1	24.6	95.7	96.4
Plateau at 48 hours	898	89.7	0.5	89.2	0.0	42.2	77.0
Plateau at 72 hours¹	889	92.3	3.8	88.5	0.0	76.1	85.4
Plateau at 72 hours (larger effect)	889	99.2	3.3	95.9	0.0	91.5	98.9
Plateau at 72 hours (higher baseline survival)	894	97.3	2.1	95.1	0.0	76.7	88.3
Constant Upslope	875	90.9	9.1	81.8	0.0	50.5	79.2
U-Shaped	897	66.5	0.0	66.5	0.7	37.6	56.5
Harmful	640	0.0	0.0	0.0	84.7	100.0	100

¹ Hypothesized scenario for power calculations

In the null scenario where there is no difference in mortality nor in VABS-3 among the survivors across any duration of cooling, we control our Type I error rate at 5% as evidenced by the 4.6% shown in the “Power” column. We are able to (correctly) declare early futility in 24.6% of the trials in the null scenario. The controlled normothermia arm is the ED95 for the null case; 95.7% of trials correctly chose either controlled normothermia or the 12-hour duration as the ED95.

In our hypothesized effect size scenario used for the primary power calculations (bolded in the table above), where cooling benefit plateaus at 72 hours (“Plateau at 72 hours”), efficacy (a cooling duration is found to be associated with better outcomes on the VABS-3 Mortality Composite Score compared to the controlled normothermia arm, based on either the early stopping for success or final evaluation criteria as detailed above) is demonstrated in 92.3% of trials. We note that in this scenario, a small percentage of simulations (3.8%) stop early due to overwhelming evidence (at least a 95% probability) that the 96-hour duration was the cooling duration with maximum effect. This finding would usually be considered a “clinically acceptable” efficacy determination, as the 96-hour dose in fact has an effect equal to the 72-hour dose. In this scenario, we have excellent power to detect duration response, and we are not frequently choosing the 96-hour duration mid-trial when the 72-hour duration performs similarly. In this scenario, we correctly identify the ED95 window (i.e. 60 hours, 72 hours, 84 hours) 76.1% of the time. Considering a “within two durations” window (i.e., 48 hours through 96 hours), we identified an acceptable ED95 in 85.4% of the trials in our primary scenario.

We maintain approximately 90% power or more in all presented scenarios assuming efficacy of longer cooling durations under different true models, except when the duration of cooling has a U-shaped response for the VABS-3 Mortality Composite Score. In this (unexpected) scenario where better outcomes are associated with mid-range durations of cooling, but then drops at the longest durations, power is limited to 66.5% to declare that any duration of cooling is associated with better outcomes than controlled normothermia, and ability to correctly choose ED95 is also limited.

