2.1 Rationale

Neurological death and disability are common outcomes in survivors of cardiac arrest. Therapeutic hypothermia to treat comatose patients resuscitated from shockable rhythms has been shown in two randomized controlled trials to markedly increase the rate of good neurological outcome, but the optimal duration of therapeutic hypothermia has not been investigated. P-ICECAP is a randomized adaptive clinical trial to characterize the duration-response curve of therapeutic hypothermia in comatose survivors of OHCA and to determine the optimal duration of cooling. There are a total of 10 possible treatment arms exploring 0 through 96 hours of cooling duration. Participants will initially be randomized to 24, 48, or 72 hours of cooling. After the first 150 participants have been enrolled, response adaptive randomization will allocate participants to additional durations from 0 through 96 hours. A zero hour cooling duration treatment arm will be opened for enrollment if there is not an increase in the treatment effect across the durations. Alternatively, longer durations (84 or 96 hours) will be opened for enrollment if the treatment effects are increasing (rather than plateauing or decreasing) through 72 hours. Comatose pediatric survivors of OHCA that have already been on

a definitive temperature control device will be enrolled. The primary outcome will be a VABS-3 Mortality Composite Score at 12 months that includes all cases by incorporating the measured VABS-3 scores in survivors and the assigned score of zero for non-survivors.

The overarching goal of this project is to identify clinical strategies (duration of cooling) that will improve the neurobehavioral outcomes of children after OHCA. We hypothesize that longer durations of cooling may improve either the proportion of children that attain a good neurobehavioral recovery or may result in better recovery among the proportion already categorized as having a good outcome. 2.2 Supporting Data

Pre-clinical data on efficacy of cooling

[figure not shown]

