Studies of the efficacy of therapeutic hypothermia in adults with OHCA used short durations of cooling. Cooling was maintained for 12 hours in one trial and for 24 hours in the two other trials. In newborns with birth asphyxia associated HIE, 72 hours is the standard of practice cooling duration. For the pediatric population, only one moderately large multicenter trial has been conducted. A duration of 48 hours was investigated which was midway between the adult 24 hours and neonatal 72 hours. For P-ICECAP, the study design will initially allocate participants to only the durations of 24 hours (the usual adult duration), 48 hours (the pediatric duration reported as safe as controlled normothermia) and 72 hours (the current standard neonatal HIE duration). As the trial continues, if the data suggest increasing efficacy with increasing duration, then the study design incrementally allocates to longer durations of cooling (up to 96 hours). Alternatively, if the data does not indicate increasing efficacy with increasing duration (or suggests an inverse relationship), the study design weights randomization toward shorter durations of cooling, including no additional cooling (controlled normothermia). This design minimizes the possibility of participants being allocated to durations of cooling that are too risky by virtue of being too short or too long and allows the study to consider a broad range of durations of cooling that would not otherwise be considered in a trial requiring fixed allocations to all treatment arms. There will be frequent interim analyses to stop the trial early for futility if no treatment arm offers a larger treatment benefit than the 0-hour duration arm.

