9. STATISTICAL CONSIDERATIONS

This trial will enroll a maximum of 900 participants. The primary outcome will be the “VABS-3 Mortality Composite Score” in which enrolled participants who die before the 12-month outcome are scored 0 and the age-adjusted standardized VABS-3 composite score is assigned for the survivors. The design of this trial is based on a statistical model of the mean VABS-3 Mortality Composite Score, i.e. the duration response curve. All participants will be receiving targeted temperature management at the time of enrollment as a condition of inclusion and will then be randomized to one of ten possible treatment arms for the duration of cooling. The ten possible treatment arms are 0, 12, 18, 24, 36, 48, 60, 72, 84, or 96-hours of cooling.

Participants will be adaptively randomized to a cooling duration, inclusive of a no additional cooling arm (controlled normothermia). The trial will determine the shortest duration of cooling that provides the maximal treatment effect and whether increasing durations of cooling are associated with better neurological outcomes. Regardless of whether participants are ever allocated to the no additional cooling arm (or have possible exposure to some pre-randomization cooling), an increasing treatment effect across some set of durations may imply a dose (duration) response effect. In this section we provide a detailed overview of the statistical design and operating characteristics. Further details are provided in the Statistical Analysis Plan (SAP).

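### Does the 92.3% power in Section 9.7 depend on which of two rules opens the 0-hour arm?

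*Protocol*

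**What the plan says.** Section 2.1 (Rationale) says: "A zero hour cooling duration treatment arm will be opened for enrollment if there is not an increase in the treatment effect across the durations". The sentence just before it says that, after the first 150 participants, response-adaptive randomization allocates to further durations anywhere from 0 to 96 hours.

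Section 3 (Study Design) puts the same idea in terms of weights: "if the data does not indicate increasing efficacy with increasing duration (or suggests an inverse relationship), the study design weights randomization toward shorter durations", with no additional cooling included among those durations.

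Section 3.2 says "After the burn in period, the trial can open all arms". It sends other durations participants when the emerging curve suggests that the largest benefit may lie there, sets proposed shares under 5% to zero until the next look, and refers to Section 9 and a statistical appendix for detail.

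Section 9.4 gives the formula: "Randomization probabilities to each treatment arm are weighted according to the weighted average of two posterior probabilities", namely being the best arm (25%) and reaching 95% of the best effect (75%). It makes no exception for 0 hours.

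Section 9.7 says that each virtual trial was "run through the entire design as specified above". It explains efficacy as the event that "a cooling duration is found to be associated with better outcomes on the VABS-3 Mortality Composite Score compared to the controlled normothermia arm". It reports 92.3% (Plateau at 72 hours) and 89.7% (Plateau at 48 hours), and summarizes: "We maintain approximately 90% power or more in all presented scenarios assuming efficacy of longer cooling durations under different true models".

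**The concern.** Read literally, Section 2.1 is a gate: the 0-hour arm stays shut while the effect rises with duration. Section 9.4 has no gate. The two part company in the scenarios used for power, where the true means rise up to 48 or 72 hours. Burn-in places nobody below 24 hours, so a gate could leave the 0-hour arm thin or empty. The headline power is nevertheless worded as a finding against controlled normothermia.

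Two things would be at stake. If the gate operates but was not simulated, the stated power could be too high. If the weights operate, Section 2.1 misdescribes to ethics boards and sites when a child can be assigned to controlled normothermia.

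**Working it through.** **1. Which rule is the design?** The Section 2.1 sentence names no probability, contrast or look at which the condition is tested, so it cannot be programmed as written. It directly follows the statement that adaptive randomization covers 0 to 96 hours. Section 3 speaks of weighting, not closure. Section 3.2 describes the posterior weighting in words and points to Section 9. Section 9.7 simulates the design set out above it, and within Section 9 the only allocation rule is 9.4. The natural reading is that the weights are the operative rule and that Table 9.7.B describes them.

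**2. Does the table's arithmetic rule out the reported power under the condition?**

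Inputs: survival p and survivor mean m from Table 9.7.A; N = 900 (Section 9.6); a 4.6% level from the null row of Table 9.7.B, taken as one-sided (z = 1.685). The survivor SD is not given for this population, so 10 to 30 is assumed.

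The composite means reproduce the table: 0.45 × 65 = 29.25 (0 h), 0.55 × 75 = 41.25 (plateau), 0.49 × 69 = 33.81 (24 h, Plateau at 72), 0.51 × 71 = 36.21 (24 h, Plateau at 48).

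Formulas:
- variance = p(SD² + m²) − (pm)²
- SE, with all 900 split in proportion to the two arm SDs, = (s₁ + s₂)/√900
- power = Φ(difference/SE − 1.685)

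Example (Plateau at 72, survivor SD 20, 24 h against plateau):
- s₁ = √(0.49 × 5161 − 33.81²) = 37.23
- s₂ = √(0.55 × 6025 − 41.25²) = 40.15
- SE = 77.38/30 = 2.579
- 7.44/2.579 = 2.885, giving 88.5%

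| Lowest arm used | Scenario | Difference | Best-case power, SD 10 / 20 / 30 |
|---|---|---|---|
| 24 h | Plateau at 72 | 41.25 − 33.81 = 7.44 | 91.4 / 88.5 / 83.6% |
| 24 h | Plateau at 48 | 41.25 − 36.21 = 5.04 | 63.7 / 59.6 / 53.8% |
| 12 h | Plateau at 72 | 41.25 − 31.02 = 10.23 | 99.5 / 99.1 / 98.0% |
| 12 h | Plateau at 48 | 41.25 − 31.49 = 9.76 | 99.1 / 98.4 / 96.8% |

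The 24-hour rows fall below the reported 92.3% and 89.7%, but they describe a trial with 0, 12 and 18 hours all closed. Section 2.1 conditions only the 0-hour arm. With that arm alone closed, the 12-hour rows apply, and both exceed the reported figures. These are ceilings under the best split, not expected power. They show only that the table's means do not contradict the reported values.

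**3. What do simulations of the two rules show?** Three approximate reconstructions used the 150 burn-in, the 25/75 weights, the 5% floor, the stopping rules and a cut-off calibrated to 4.6% under the null. The priors, survivor SD and late-efficacy cut-off are assumed. Power for Plateau at 72:

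| Reconstruction | Weights alone | Condition added |
|---|---|---|
| A: six prior and tie settings, survivor SD 25, 1,000 trials per cell | 64-97% | 50-73% |
| B: prior that 0 h is best 0.35-0.5, 500-800 trials per cell | 93-97% | strict gate on model probability 69-79%; on observed means 58-65%; gate that stays open once triggered 73-85%; closed only if a rise is at least 80% probable 86-95% |
| C: prior 0.35, survivor SD 20, 250 trials per cell | 98% | closed if a rise is over 50% probable 91%; over 80% probable 96% |

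For Plateau at 48, C gave 98% with weights alone, then 93% and 98% with the condition at 50% and 80%. With a weaker prior of 0.18, B gave 78% on weights alone, so neither rule reached 92.3%. None of these reproduces Table 9.7.B: null futility in A was 0-7% against the stated 24.6%, and B found no early success against the stated 3.8%.

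**The case for a change.** The best case for a change is that both wordings are current protocol text, so this is not something left to the SAP. Reconstruction A, in its three settings closest to the reported power, fell from 94-97% to 57-73% under a literal condition, and across its settings the share of planning trials with nobody at 0 hours reached 32-66%. Reconstruction B used different priors and curve shapes, and its prior-0.5 runs with one shape library matched the stated futility well (25-26%). It agreed on direction in its main settings. With 0 hours never opened it gave only 60-64%, because adaptive weights send few children to 12 and 18 hours. A high ceiling therefore does not guarantee high power.

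Much of this stands. The wordings differ, and a strict gate on the 0-hour arm would probably cost power, possibly a lot. What does not stand is the step from there to a doubtful 92.3%. That needs the gate to be a real rule, and the protocol gives no form in which it could be run. The codings are outside choices, and the result moves from 58% to 96% with the coding and the priors. In A, the weights alone missed 92.3% in three of six settings (86.3, 76.7 and 64.2%), so the assumed priors and tie rules matter about as much as the gate.

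The two side issues are already covered. Sections 5.1, 9 and 11.5 disclose possible assignment to controlled normothermia without the condition. That the comparison is model-based is stated in Sections 3 and 9.3.1 and in the 9.7 definition of power. Section 9 adds that a duration response may be inferred "Regardless of whether participants are ever allocated to the no additional cooling arm", and the Background disclaims specifically addressing superiority over normothermia.

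**Conclusion.** No change to the plan follows. Read together, Sections 2.1, 3, 3.2 and 9.4 describe one adaptive rule at different levels of detail, and Section 9.7 simulated the rule in Section 9. On that reading 92.3% and 89.7% stand as stated. The means in Table 9.7.A do not contradict them even if the 0-hour arm alone were closed (ceilings 98.0-99.5% and 96.8-99.1%, survivor SD 10-30).

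The conclusion rests on Section 9.4 being the operative rule, which is an inference from the structure of the document; the SAP was not available to confirm it. If a separate gate were in use, power for Plateau at 72 could fall by 2 points (98% to 96%, lenient coding in C) or by 38 points (95.2% to 57.1%, strict coding in A). Nothing in the protocol specifies such a gate. The Section 2.1 sentence is loosely worded, and tidying it would alter no allocation, stated power or conclusion.
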